11.6.2.11 Gonioscopy

Gonioscopy to assess the iridocorneal angles will be performed at SDTP baseline (Day -2; Cohort A only), MDTP baseline (Day -2; Cohorts B, C, and D), and on Day 29. Gonioscopy should be performed after the corneal epithelium has been evaluated for defects with fluorescein and after IOP has been measured but before dilated posterior segment examination (Day 29).

The number and percentage of subjects by Shaffer grading system at position 12:00 to 3:00, 3:00 to 6:00, 6:00 to 9:00, and 9:00 to 12:00 will be summarized by eye (study eye, non-study eye, and either eye (MDTP only)) and treatment group at each visit and time point. For either eye summaries, the eye with the lower Shaffer grade will be summarized. The denominator of the percentage is the number of subjects who have the assessment for the specified eye and visit. Results of gonioscopy will be listed by individual subject.

11.6.2.12 Noncontact Specular Microscopy

Noncontact specular microscopy will be performed, with the subject seated, to assess endothelial cell count at the following visits:

- Screening
- SDTP (Cohort A only): baseline (Day -1) and Day 2
- MDTP (all cohorts): baseline (Day -1) and Days 14 and 29.

Details of the procedure will be found in the ophthalmology procedures manual.

For each eye and timepoint assessed, three measurements of central endothelial cell density (cells/mm²) will be made. All measurements will be recorded in the source document and eCRF and the mean of the 3 readings for each eye will be used to determine the mean cell density at the given time point for each eye. These mean density values will be used for all specular microscopy analyses of cell density.

Baseline specular microscopy cell density is defined as the mean of the 3 readings on Day -1. Descriptive statistics for the mean central endothelial cell density and changes from baseline at each assessment time point will be presented by eye (study eye, non-study eye, and either eye (MDTP only)) and treatment group. For either eye summaries, the eye with the smaller cell density will be summarized at baseline. For post baseline assessment, the eye with the greater

decrease from baseline will be summarized. If both eyes have the same change from baseline, the eye with the smaller value will be summarized. Results of noncontact specular microscopy will be listed by individual subject.

11.6.2.13 Corneal Pachymetry

Corneal pachymetry to assess central corneal thickness will be performed after the predose examination. With the pachymeter set to perform a single measurement, the investigator will take and record 3 consecutive measurements at each applicable time point at the following visits:

- Screening
- SDTP (Cohort A only): baseline (Day -1) and Days 1 and 2
- MDTP (all cohorts): baseline (Day -1) and Days 1, 2, 7, 14, 28, and 29.

If the range of the measurements is 15 microns or less, the set of readings is acceptable; if not, all measurements are discarded and repeated until an acceptable set of 3 measurements is obtained. The set of all 3 measures are recorded in the source document. The mean of the 3 measurements made at each timepoint are the values that will be used for analysis.

See [Table 2](#), [Table 3](#), [Table 4](#), and [Table 5](#) for detailed timings by cohort. Baseline corneal thickness is defined as the average of the mean of measures at 5 time points (pre-dose, and hours 1, 2, 4, 12) on Day -1. Descriptive statistics for the mean central corneal thickness and change from baseline at each assessment time point will be presented by eye (study eye, non-study eye, and either eye (MDTP only)) and treatment group. In addition, descriptive statistics for the percentage change from baseline at each assessment time point will be presented by eye (study eye, non-study eye, and either eye) and treatment group for MDTP only. For either eye summaries, the eye with the smaller corneal thickness will be summarized at baseline. For post baseline assessment, the eye with the greater decrease from baseline will be summarized. If both eyes have the same change from baseline, the eye with the smaller value will be summarized. Results of corneal pachymetry will be listed by individual subject.

12. CLINICAL PHARMACOKINETIC AND PHARMACODYNAMIC ANALYSES

12.1 Pharmacokinetics Population and Pharmacodynamic Population

Pharmacokinetic Set

The PK set will consist of all subjects in the Safety set for whom the primary PK data are considered sufficient and interpretable.

Pharmacodynamic Set

The PD set will consist of all subjects in the Safety set for whom the primary PD data are available.

12.2 Pharmacokinetic Methods

All summaries and analyses of the PK data will be based on the Pharmacokinetic Set.

12.2.1 Concentration Data

Serial blood samples will be collected from each subject during this study to allow for the determination of the PK of SHP639 administered as SHP639 ophthalmic solution. Blood samples for PK analysis of SHP639 will be drawn according to the following schedule:

SDTP (Cohort A only): Day 1 - Predose, 30 min, 1, 2, 3, and 6 h

MDTP (all cohorts): For Days 1 and 27 - Predose, 30 min, 1, 2, 3, and 6 h

Plasma samples will be analyzed to determine the concentrations of SHP639 using a validated bioanalytical method based on liquid chromatography with mass spectrometry.

Individual plasma concentrations and time deviation data will be presented in a data listing. Plasma concentration data will be summarized by scheduled time-point using the following descriptive statistics: number of observations (n), arithmetic mean, standard deviation (SD), median, geometric mean, coefficient of variation (CV), minimum, and maximum.

The individual and mean plasma SHP639 concentration versus time profiles will be presented in figures on both linear and semi-logarithmic scales. Mean plasma concentration versus time profiles will be presented using nominal time and individual plasma concentration versus time profiles will be presented using actual time.

12.2.2 Handling Below the Limit of Quantification Values

All plasma concentration values below the limit of quantification (BLQ) will be set to zero when calculating summary statistics.

For the calculation of PK parameters all plasma concentrations that are BLQ prior to the first measurable concentration will be set to zero. The BLQ values that are between measurable concentrations will be set to missing. The BLQ values following the last quantifiable time-points will be set to missing. No concentration estimates will be imputed for missing sample values. Any sample with a missing value will be treated as if the sample had not been scheduled for collection and will be ignored when calculating mean concentrations or PK parameters.

12.2.3 Pharmacokinetic Parameters

The following plasma PK parameters will be calculated for SHP639 on Day 1 for SDTP (Cohort A only) and on Day 1 and Day 27 for MDTP (all cohorts) by non-compartmental method using Phoenix[®] WinNonlin[®] version 6.4 or higher (Certara USA, Inc., Princeton, NJ).

Parameter	Definition
C_{max}	Maximum observed plasma concentration
T_{max}	Time to reach maximum observed plasma concentration
$AUC_{0-\infty}$	Area under the plasma-concentration time curve from time 0 extrapolated to infinity, calculated using the linear up/ log down trapezoidal rule
AUC_{0-t}	Area under the plasma-concentration time curve from time 0 to the last measurable concentration, calculated using the linear up/ log down trapezoidal rule
$AUC_{0-\tau}$	Area under the plasma-concentration time curve over a dosing interval for each multiple-dose regimen, calculated using the linear up/log down trapezoidal rule (Day 1 and Day 27 for MDTP of all cohorts)
$t_{1/2}$	Apparent first-order terminal elimination half-life, calculated as $t_{1/2} = \ln 2 / K_{el}$
K_{el}	Elimination rate constant estimated from the linear regression of the natural log-transformed concentration over time at the terminal phase.
$\%AUC_{ex}$	Percentage of the area extrapolated for calculation of $AUC_{0-\infty}$
CL/F	Apparent clearance, calculated as $Dose / AUC_{0-\infty}$ for Day 1 for SDTP (Cohort A only) and $Dose / AUC_{0-\tau}$ for Day 27 for MDTP (all cohorts)
V_z/F	Volume of distribution, calculated as $V_z/F = (CL/F) / \lambda_z$
$R_{ac}(C_{max})$	Accumulation ratio based on C_{max} for each multiple-dose regimen, calculated as $C_{max} (Day 27) / C_{max} (Day 1)$
$R_{ac}(AUC)$	Accumulation ratio based on AUC for each multiple-dose regimen, calculated as $AUC_{0-\tau} (Day 27) / AUC_{0-\tau} (Day 1)$

All calculations for PK analysis will be based on actual sampling times. All PK analyses will be conducted by the Department of Clinical Pharmacology, PPD, Inc, Richmond, VA, USA.

All PK parameters will be presented in data listings and summarized in tables by dose, cohort, treatment, and study day, using descriptive statistics (n, mean, SD, median, maximum, minimum, geometric mean, and CV%). Geometric means will be reported for AUCs and C_{max} only.

12.3 Statistical Analysis of Pharmacokinetic Data

For each of SD, QD, BID, TID and QID dosing regimens, if sufficient data are available across dose groups, dose proportionality of plasma SHP639 PK variables $AUC_{0-\infty}$, AUC_{0-t} , $AUC_{0-\tau}$, and C_{max} over the dose ranges tested will be investigated. For Days 1 and 27 for MDTP of all cohorts, the following power model will be used to assess dose proportionality. The model is defined as:

$$\ln(\text{PK parameter}) = a + b * \ln(\text{dose}),$$

where 'a' is the intercept and 'b' is the slope of the line. The 95% confidence interval (CI) of the estimate of parameter 'b' will be presented. A 95% CI of the slope that includes 1.0 will be interpreted as the absence of significant evidence of non-proportionality.

For statistical analysis of accumulation of SHP639, a linear mixed-effect model with day, dose, and day and dose interaction term as fixed effects and subject as random effect will be fitted to the natural log-transformed C_{max} and $AUC_{0-\tau}$ to construct 95% CIs for Day 27 compared with Day 1 for each of QD, BID, TID, and QID dosing regimens separately. Statistical analysis to assess dose proportionality and accumulation of SHP639 will be conducted using SAS for Windows® (Version 9.3 or higher).

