9.8.1.1 Pharmacokinetic Endpoints

If data permit, PK parameters will be estimated as appropriate and may include, but are not limited to, the following:

- Maximum observed concentration (C_{\max})
- Time to reach C_{\max} (t_{\max})
- Area under the observed concentration vs time curve:
 - From time zero (predose) to the time of the last measurable concentration (AUC_{0-t})
 - Over the dosing interval ($AUC_{0-\tau}$) for each multiple-dose regimen including QD, BID, TID, and QID
 - From time zero (predose) extrapolated to infinity ($AUC_{0-\infty}$) for QD dosing
- Apparent terminal phase elimination half-life ($t_{1/2}$)
- Apparent clearance (CL/F)
- Apparent volume of distribution (V_z/F)
- Accumulation ratio based on AUC for each multiple-dose regimen, calculated as $AUC_{0-\tau}$ (Day 27)/ $AUC_{0-\tau}$ (Day 1) ($R_{ac[AUC]}$)
- Accumulation ratio based on C_{\max} for each multiple-dose regimen, calculated as C_{\max} (Day 27)/ C_{\max} (Day 1) ($R_{ac[C_{\max}]}$)

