^m Drop comfort assessments will be performed immediately and 1, 2, and 3 minutes after instillation of the investigational product; to be assessed at morning doses only. If the score is not ≤ 3 at minute 3, the drop comfort assessment should be repeated at minutes 5, 10, and 15 until the score is ≤ 3 . If the score is >3 at minute 15, it should be recorded as an adverse event.

ⁿ If BCVA decreases by 6 or more letters, then a dilated posterior segment examination should be performed.

^o Manifest refraction should be repeated if the BCVA in either eye decreases by 10 or more letters.

^p Conjunctival redness will be evaluated using the Efron scale.

^q SDTP dosing (Cohort A only): investigational product (SHP639 ophthalmic solution or placebo) will be administered once on the morning of Day 1. MDTP dosing: Cohort A=once daily, Cohort B=twice daily, Cohort C=3 times daily, Cohort D=4 times daily; the final dose will be administered on the morning of Day 28. Dose administration will occur during waking hours.

^r The Day 88 visit is 60 days post last dose (Day 28 of MDTP).

^s For Screening, MWOA, and Day 29 visits only one round of ophthalmic assessments needs to be done in the morning.

^t At check-in for overnight stays the following assessments will be performed: physical exam, drugs of abuse screening, alcohol breathalyzer, vital signs, hematology, chemistry, urinalysis, and a single ECG.

^u The Day 88/FU visit is labeled "Day 88" based on a subject's duration of participation from Day 1 (1st dose) of the MDTP. Subjects in cohort A1, A2, and A3 will have been in the study for a longer duration due to the SDTP.

^v At screening IOP may be done at any time during the day. At MWOA (D-14), IOP should be done at 10:00am +3 hours. IOP only needs to be done at one time during screening, MWOA, and Day 29.

Table 2 Detailed Schedule of Events – Cohort A

Assessment	Days Performed (Screening-D29) ^f	Predose/ Morning ^a	0 m	30 m	1 h	2 h	3 h	4 h	6 h	8 h	12 h
		Gonioscopy ^c	SCR, D29.	X							
Specular microscopy, noncontact	SCR. SDTP: D-1, D2. MDTP: D-1, D14, D29.	X									
Corneal pachymetry	SCR. SDTP: D-1, D1, D2. MDTP: D-1, D1, D2, D7, D14, D29.	X			X	X		X			X
Antidrug Ab blood sampling	D-2, D14, D29, D88/FU	X									
Drugs of abuse	SCR, D-14, SDTP: D-2, MDTP: D-2 and D-1, D1, D14, D21, D26.	X									
Alcohol breath test	SCR (D-42), SCR (D-14). SDTP: BL (D-2), MDTP: BL (D-2 and D-1), D1, D14, D21, D26.	X									

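### The SAP calculates and models AUC0-inf for every multiple-dose regimen on Days 1 and 27; the documents disagree on its scope, on Day 27 it carries earlier doses, and for QID it is probably not estimable.

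*SAP*

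**What the plan says.** SAP 12.2.3 lists AUC0-inf, half-life and the elimination rate constant among parameters to be calculated for the single-dose period and "on Day 1 and Day 27 for MDTP (all cohorts) by non-compartmental method", with no limit by regimen. SAP 12.3 then covers proportionality "For each of SD, QD, BID, TID and QID dosing regimens, if sufficient data are available across dose groups", names AUC0-inf as one of four variables, and adds "For Days 1 and 27 for MDTP of all cohorts, the following power model will be used to assess dose proportionality".

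Protocol 9.8.1.1 assigns AUC0-tau to all four multiple-dose regimens. The next line reads "From time zero (predose) extrapolated to infinity ($AUC_{0-\infty}$) for QD dosing". The list is open-ended. The protocol synopsis names AUC0-inf with no QD limit, and both the synopsis and protocol 9.8.1.2 include it in the power model.

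Sampling in SAP 12.2.1 is "MDTP (all cohorts): For Days 1 and 27 - Predose, 30 min, 1, 2, 3, and 6 h". On dose timing, the SAP 2.2 schedule says "Dose administration will occur during waking hours", and protocol 6.2.3.1 puts the first daily dose between 7 and 9 am. The text available gives no interval between doses.

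For CL/F, SAP 12.2.3 uses AUC0-inf only for the single-dose period and AUC0-tau for Day 27.

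**The concern.** AUC0-inf after one dose measures the exposure from that dose. Two features of the plan can break that meaning.

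First, by Day 27 drug from earlier doses may still be present, and extrapolating to infinity adds it to the morning dose. The SAP avoids this for CL/F but keeps AUC0-inf in the Day 27 proportionality model.

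Second, if a further dose falls before the last sample, the 6 h concentration belongs to two doses. The SAP has rules for values below quantification and reports the percentage extrapolated. It sets no acceptance limit on that percentage, no rule for choosing terminal-phase points, and no exclusion of samples drawn after the next dose.

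At stake are the reported AUC0-inf, half-life and AUC0-t for the most frequent regimens, and an analysis scope on which the protocol does not agree with itself.

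**Working it through.** **1. The plan's own figure.** Six sampling times over two MDTP days give 12 samples, and 12 × 4 mL = 48 mL (Cohorts B to D). Adding the single-dose day for Cohort A gives 18 samples and 72 mL. Both match protocol Tables 11 and 12, which confirms six samples per PK day; SAP 12.2.1 puts the last at 6 h.

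**2. Scope of AUC0-inf, side by side.**

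| Place | Scope of AUC0-inf |
|---|---|
| Protocol synopsis | no regimen limit; in the power model |
| Protocol 9.8.1.1 | QD, in an open-ended list |
| Protocol 9.8.1.2 | in the power model, no limit |
| SAP 12.2.3 | SDTP Day 1; MDTP Days 1 and 27, all cohorts |
| SAP 12.3 | SD, QD, BID, TID, QID, if data suffice |

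**3. Day 27 carry-over.** Take n doses per day at gap g starting in the morning, then an overnight gap, with mono-exponential decline at rate k = ln 2 / half-life. By superposition at steady state, Day 27 AUC0-inf divided by single-dose AUC0-inf is

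F = 1 + [sum over j = 0 to n−1 of exp(−k(24 − jg))] / [1 − exp(−24k)].

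QID, half-life 4 h, doses over 12 h (g = 4): (2^−6 + 2^−5 + 2^−4 + 2^−3) / (1 − 2^−6) = 0.2344 / 0.9844 = 0.238, so F = 1.24. Over 16 h (g = 5.33): (2^−6 + 2^−4.667 + 2^−3.333 + 2^−2) / 0.9844 = 0.4042 / 0.9844 = 0.411, so F = 1.41.

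| Assumed half-life | QD | BID, 12 h apart | TID over 12–16 h | QID over 12–16 h |
|---|---|---|---|---|
| 1 h | 1.00 | 1.00 | 1.00 | 1.00 |
| 2 h | 1.00 | 1.02 | 1.02–1.07 | 1.02–1.07 |
| 4 h | 1.02 | 1.14 | 1.19–1.33 | 1.24–1.41 |

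At 6 h the QID factor is 1.61 to 1.84. On Day 1 of the MDTP, Cohorts B to D have no earlier dose and Cohort A follows a 3 to 14 day washout, so F = 1 at these half-lives. The QID column is carry-over alone; step 5 governs if the second dose comes before 6 h.

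**4. Effect on the slope.** With linear kinetics, AUC = F × c × dose, so ln(AUC) = ln(F × c) + 1 × ln(dose). F enters intercept a (ln 1.41 = 0.34) and b stays 1.00. The model is fitted within regimen, so F is common to its dose levels. Carry-over also leaves half-life unchanged in this model, because the residual drug declines at the same rate k.

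**5. Second QID dose against the 6 h sample.** With equal gaps, the second of four doses falls at span/3, where span is the time from first to last dose: 12/3 = 4.0 h, 14/3 = 4.67 h, 16/3 = 5.33 h. It precedes 6 h unless the span reaches 18 h. A 7 am first dose would then put the last at 1 am. TID gaps are span/2 = 6 to 8 h, so the 6 h sample is normally clear.

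Illustration (assumed one-compartment model, absorption rate 3/h, unit dose and volume): C(t) = [3/(3 − k)] × [exp(−kt) − exp(−3t)]. At half-life 2 h (k = 0.347), C(3) = 1.131 × 0.3534 = 0.400 and C(6) from the first dose = 1.131 × 0.125 = 0.141. A second dose at 4.67 h adds C(1.33) = 1.131 × 0.612 = 0.692. The 6 h value is 0.834, or 2.1 times the 3 h value, where one dose would give 0.35 times. Across half-lives 0.5 to 8 h and second doses at 4 to 5.33 h, the Day 1 ratio is 1.8 to 17. There is no declining phase through the last sample, and the terminal slope was not estimable on Day 1 or Day 27 in any case tried. Day 1 AUC0-t is 1.3 to 2.2 times its one-dose value.

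**The case against.** The strongest reply is that little depends on this. The SAP fits are conditional on sufficient data, nonclinical systemic exposure was very low or undetectable (protocol 1.2.1), PK tables are not interim outputs (SAP 16), and the PK-PD objective is exploratory. That stands, and it limits the weight of the point. The data condition does not remove the QID problem, though: a sample taken soon after a second dose is more likely to be measurable.

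A reader might infer that the SAP breaches a firm QD-only rule. The documents do not support that. The limit appears only in protocol 9.8.1.1, in an open-ended list, and the synopsis and 9.8.1.2 omit it. The adjacent contrast with AUC0-tau makes the limit look deliberate, but the protocol itself is not uniform.

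A reader might also infer that the proportionality slope is wrong, or that half-life is wrong in every multiple-dose regimen. Step 4 shows neither follows from carry-over. Biasing b needs a dose-dependent cause, such as loss of low-dose samples below quantification or nonlinear kinetics.

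Finally, the early second QID dose is not stated. A first gap of 6 h with shorter later gaps fits a waking day, and the cohort schedules are only partly legible. Roughly equal gaps are the natural reading, but the point must stay conditional on the recorded times.

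**Conclusion.** The point holds in a limited form. The scope of AUC0-inf differs between protocol 9.8.1.1 and the synopsis, protocol 9.8.1.2, SAP 12.2.3 and SAP 12.3. Day 27 AUC0-inf is not a single-dose exposure in any regimen with carry-over. For QID the inflation is negligible to 7% at half-lives of 1 to 2 h and 24 to 41% at 4 h.

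These sizes rest on assumed half-lives, which the documents do not give, and on equal daytime gaps with an overnight break. Assuming a constant 6 h QID interval would give 1.55 at 4 h, but this ignores the overnight gap that waking-hours dosing implies.

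If the second QID dose falls at about 4 to 5.3 h, the larger problem is that QID half-life and AUC0-inf cannot be obtained meaningfully and AUC0-t covers parts of two doses. The impact is modest: PK is descriptive, and no decision in the plan rests on AUC0-inf.

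**What to change.** - Drop AUC0-inf from the Day 27 summaries and power model and use AUC0-tau there. Define tau from the recorded dose times. With sampling ending at 6 h, AUC0-tau also needs extrapolation for the longer intervals, and the SAP should say how.
- Limit AUC0-inf to the SDTP and the first-dose QD profile. Day 1 BID and TID values have no carry-over; leaving them out is for agreement with protocol 9.8.1.1, not to correct a bias.
- In any regimen where recorded times show a further dose before the last PK sample, exclude samples after that dose from AUC0-t and the terminal-slope fit.
- Keep half-life for BID, and for TID where no second dose precedes 6 h. CL/F needs no change.
- Align the protocol synopsis, protocol 9.8.1.1 and 9.8.1.2, and SAP 12.2.3 and 12.3.

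The cost is wording and fewer tables. No new data are needed, because in-clinic dosing times already go into the eCRF (protocol 6.5). QID half-life may go unreported.

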12.4 Pharmacodynamic Methods

All the PD analyses will be performed using the Pharmacodynamic set. Intraocular pressure (IOP; mmHg), a PD biomarker, will be measured using Goldmann applanation tonometry.

Intraocular pressure will be measured according to the following schedule:

SDTP (Cohort A only): baseline (Days -2 and -1), Days 1 and 2, at Predose, 0.5, 1, 2, 3, 4, 6, 8, and 12 h

MDTP (Cohort A only): (all cohorts): baseline (Days -2 and -1), Days 1, 2, 27, and 28, at Predose, 0.5, 1, 2, 3, 4, 6, 8, and 12 h

MDTP (all cohorts): Days 7, 14, and 21 at Predose, 2, 4, 8, and 12 h

The individual and mean absolute IOP, IOP reduction from baseline and percentage of IOP reduction from baseline versus time profiles will be presented in figures. Mean plots will be presented using nominal time and individual plots will be presented using actual time.

In addition, the relationship of percentage of IOP reduction from baseline and dose of SHP639 will be presented in a Box-and-Whiskers plot.

Percentage of IOP reduction from baseline measurements data versus time will be used to estimate the PD parameters using Phoenix® WinNonlin® version 6.4 (Certara USA, Inc., Princeton, NJ) for each individual in each treatment by eye (study eye and non-study eye). Baseline is defined as the arithmetic mean of the time-matched IOP measurements on Days -2

and -1 for that particular subject. Potential effect of diurnal change on variation in IOP is accounted for by factoring time-matched baseline in the calculations of percent of IOP reduction from baseline measurements.

Parameter	Definition
IOP reduction from baseline	IOP reduction from baseline is calculated as follows: $\frac{\text{Baseline IOP} - \text{IOP after treatment}}{\text{Baseline IOP}}$
% of IOP reduction from Baseline	Percentage of IOP reduction from baseline is calculated as follows: $\frac{(\text{Baseline IOP} - \text{IOP after treatment})}{\text{Baseline IOP}} \times 100$
E _{max}	Maximum percent IOP reduction from baseline
TE _{max}	Time of E _{max}
AUEC _{0-t}	Area under the effect curve for the percentage of IOP reduction from baseline versus time profile from time zero (predose) to the time of the last measurable percentage of IOP reduction from baseline, calculated using the linear up/log down interpolation rule.
AUEC _{0-τ}	Area under the effect curve for the percentage of IOP reduction from baseline versus time profile over a dosing interval, calculated using the linear up/log down interpolation rule.
AUEC _{0-∞}	Area under the effect curve for the percentage of IOP reduction from baseline versus time profile from time zero (predose) extrapolated to infinity, calculated using the linear up/log down interpolation rule.

